ACTG NETWORK COORDINATING CENTER
Social & Scientific Systems, Inc., a DLH Holdings Company
[name]
[name] [name]
[contact]

LETTER OF AMENDMENT #1

DATE: June 22, 2023
TO: ACTG CTU Principal Investigators, CRS Leaders, and CTU/CRS Coordinators
FROM: A5362 Protocol Team
SUBJECT: Letter of Amendment #1 for Protocol A5362, Version 2.0

The following information affects the A5362 study and must be forwarded to your institutional review board (IRB)/ethics committee (EC) as soon as possible for their information and review. This Letter of Amendment (LOA) should be implemented immediately, prior to IRB/EC approval, to eliminate immediate hazard to participants.

The following information also affects the Sample Informed Consent (SIC). A letter informing participants about the contents of this LOA and an addendum to the SIC were provided electronically to sites on 16Jun2023.

Sites should implement the LOA immediately and inform IRB/EC and any other applicable regulatory entities of the LOA. Sites are still required to submit an LOA registration packet to the DAIDS Protocol Registration Office (PRO) at the Regulatory Support Center (RSC). Sites will receive a registration notification for the LOA once the DAIDS PRO verifies that all required LOA registration documents have been received and are complete. An LOA registration notification from the DAIDS PRO is not required prior to implementing the LOA. A copy of the LOA registration notification, along with this letter and any IRB/EC correspondence, should be retained in the site's regulatory file.

In April 2023, the study temporarily closed to screening and accrual due to an unanticipated trend in outcome events, which triggered review by the National Institute of Allergy and Infectious Diseases (NIAID) Therapeutic and Prevention Data and Safety Monitoring Board (DSMB), which met on 01Jun2023 to review all available safety and efficacy data from A5362. The DSMB recommended that A5362 permanently close to accrual because of the high rate of treatment failure and TB recurrence. There were no other safety concerns related to study regimen. The A5362 team, NIAID and DAIDS leadership, and ACTG leadership concur with the following DSMB recommendations for implementation:

- Permanently close A5362 to accrual.

- Participants currently receiving treatment in the experimental arm (Arm 1) should finish their 3-month experimental regimen [rifapentine/isoniazid/pyrazinamide/ethambutol/clofazimine (PHZEC)] and then be placed on an additional 3 months of continuation phase rifampicin/isoniazid (RH) regimen.
- Participants in Arm 1 who have already finished the experimental regimen in Arm 1 without an unfavorable outcome, should be followed closely for the duration of the trial. The DSMB suggests that the investigators consider strategies for more intensive follow-up of these participants to ascertain recurrences, and that those diagnosed with recurrence be referred for 6 months of SOC treatment.
- Participants in Arm 1 follow-up will be extended to 117 weeks, as outlined below.

As referenced in the investigator and IRB/EC letters sent to A5362 sites on 16Jun2023, this LOA formally outlines changes to Version 2.0 of A5362, dated 08Jul2022, given the abovementioned DSMB recommendations.

There are no changes to the Sample Informed Consent (SIC) in this LOA. Refer to the SIC addendum for the updated information to provide to participants and for reconsenting participants.

This LOA also includes revisions from the 26Sep2022 DSMB review, in which the DSMB requested that the team specify the monitoring of the unfavorable composite outcome per definition 10.2.4A.

TABLE OF CONTENTS

| | |
|-------------------------------------------------------------|---|
| 1. Section SCHEMA, DESIGN..... | 4 |
| 2. Section SCHEMA, DURATION..... | 5 |
| 3. Section SCHEMA, REGIMEN..... | 5 |
| 4. Section 1.4, Exploratory Objectives | 5 |
| 5. Section 3.0, STUDY DESIGN..... | 5 |
| 6. Section 6.1, Schedule of Evaluations | 6 |
| 7. Section 6.2.3 Post-Entry Evaluations..... | 7 |
| 8. Section 6.3, Instructions for Evaluations | 7 |
| 9. Section 10.5.1, Interim Monitoring Guidelines..... | 7 |
| 10. Section 10.5.2, Interim Analysis Plan | 7 |
| 11. Appendix I-C, ADDENDUM TO SAMPLE INFORMED CONSENT | 8 |
| 12. Protocol Signature Page (PSP) | 8 |

The following are changes (noted in bold or strikethrough) to A5362, Version 2.0, 08Jul2022, titled A “Phase IIc Trial of Clofazimine- and Rifapentine-Containing Treatment Shortening Regimens in Drug-Susceptible Tuberculosis: The CLO-FAST Study.” These changes will be included in the next version of the A5362 protocol if it is amended at a future date. Changes that have already been made (Clarification Memo #1) have been incorporated in the excerpted text shown below (and are no longer presented in bold or strikethrough).

1. Section SCHEMA, DESIGN

The following information has been added to reference the change in study design due to a DSMB review.

Per the June 1, 2023 DSMB review, and permanent closure of accrual, the follow-up schedules for Arm 1 participants will be revised as follows:

- Participants currently on Arm 1 study treatment should complete the 3-month regimen and then be placed on an additional 3 months of continuation phase rifampicin/isoniazid (RH). Based on the DSMB recommendations, an additional 3 months of treatment is necessary to decrease the likelihood of treatment failure and TB relapse in study participants.
- Participants who have already completed Arm 1 treatment should be seen for a follow-up visit within the next 4 weeks of the date of this LOA, at a scheduled or unscheduled visit, to assess whether further treatment is needed.
- Additional extended follow-up visits for participants in Arm 1 will be added at weeks 30, 38, 60, 91 and 117 unless the participant has already been referred for, or already received, 6 months of SOC through the local TB program. The additional visits at weeks 30, 38, and 60 may be performed by telephone only; these calls are to assess the participant’s TB symptoms and determine if it is clinically indicated that the participant should come in for an in-person visit to assess the need for possible poor treatment response (PPTR) assessments and/or referral to SOC treatment.
- If the site investigator diagnoses TB recurrence at any time during Arm 1 follow up, the participant should be referred to 6 months of SOC treatment by the national TB program. For study purposes, such participants should continue to be followed in the study for outcome determination, unless the participant withdraws consent.

Participants in Arm 2 and Arm C should complete their treatment and follow-up schedule as planned; no additional visits are planned for these groups.

2. Section SCHEMA, DURATION

Arm 1:

- Up to 117 weeks.
- 65 weeks for participants who are or have been diagnosed with TB treatment failure or recurrence and are or have been referred to six months of local SOC treatment by the national/local TB program.

Arm 2: 65 weeks

Arm C: 65 weeks

3. Section SCHEMA, REGIMEN

The following paragraph has been included to add three months of rifampicin/isoniazid for Arm 1 participants who are currently receiving the experimental 3-month treatment regimen as of 16Jun2023. The treatment regimen for all other participants will remain the same.

Arm 1 participants receiving the experimental 3-month treatment regimen as of 16Jun2023:
rifapentine/isoniazid/pyrazinamide/ethambutol (PHZE) + clofazimine (CFZ) 300 mg once daily for 2 weeks; then PHZE + CFZ 100 mg once daily for 6 weeks; then rifapentine/isoniazid/pyrazinamide (PHZ) + CFZ 100 mg once daily for 5 weeks; then rifampicin/isoniazid (RH) for 13 weeks for a total of 26 weeks of study treatment.

4. Section 1.4, Exploratory Objectives

The following objective has been added to align with the addition of Drug-Susceptibility Testing and Sputum AFB Smear and Culture at weeks 91 and 117:

1.4.8 To explore long term outcomes in Arm 1 participants through 117 weeks after randomization.

5. Section 3.0, STUDY DESIGN

The following update to the Arm 1 regimen and follow-up has been added to the end of the section:

Updates following the DSMB reviews in April and June 2023

Following the DSMB reviews in April and June 2023, and the premature closure to accrual of the study, Arm 1 treatment duration and follow-up was revised for participants who are currently on or have completed Arm 1 study treatment without experiencing treatment failure or TB recurrence, and have not already been referred to six months local SOC treatment. Participants in Arm 1 who have not already been referred to six months local SOC treatment will have follow-up extended through week 117.

6. Section 6.1, Schedule of Evaluations

A new Table 6.1-2 has been inserted for the additional visits and assessments for Arm 1 after week 26. The SOE table for Arm C has been renumbered to Table 6.1-3.

Table 6.1-2: Schedule of Evaluations for Arm 1 Who Have Not Been Referred to Local SOC, Additional Visits and Assessments After Week 26

| Evaluation | Follow-up | | | | | | | | | After Week 65 | |
|--------------------------------------------------------------|------------------------------|----------------------|-----------------|----------------------|----------------------|-----------------|----------------------|-------------------------------|-----|------------------------------------------------------------------------------|-------------------------------------------|
| | Visit Window is ± 7 days | | | | | | | Visit Window is ± 14 days | | Time of Suspected Treatment Failure or Recurrence or Poor Treatment Response | Premature Treatment/Study Discontinuation |
| | 30 ⁴ | 34 | 38 ⁴ | 42 | 52 | 60 ⁴ | 65 | 91 | 117 | | |
| Targeted Physical Exam | (X) | Refer to Table 6.1-1 | (X) | Refer to Table 6.1-1 | Refer to Table 6.1-1 | (X) | Refer to Table 6.1-1 | X | X | X | X |
| Concomitant Medications | (X) | | (X) | | | (X) | | X | X | X | X |
| Pregnancy Testing | As clinically indicated | | | | | | | | | | |
| Sputum AFB Smear and Culture ¹ | (X) | Refer to Table 6.1-1 | (X) | Refer to Table 6.1-1 | (X) | (X) | Refer to Table 6.1-1 | X | X | X | X |
| Molecular Assay to Detect Mtb INH- and RIF-Resistance | (X) | | (X) | | (X) | (X) | | X | X | X | X |
| Whole Genome Sequencing ² | | | | | | | | | | X | X |
| Drug-Susceptibility Testing ³ | (X) | | (X) | | (X) | (X) | | X | X | X | X |
| TB Symptom Assessment (See Section 6.3.18) | X | | X | | X | | | | | | |

(X) = If clinically indicated.

- 1 Two sputum samples for AFB smear microscopy and culture in liquid and solid media will be collected at each time point. Sputum specimens and culture isolates will be stored for targeted deep sequencing and phenotypic drug-susceptibility testing in the event of TB treatment failure or TB recurrence.
- 2 For participants with suspected recurrence, whole genome sequencing performed on the baseline and recurrent isolate pair.
- 3 See [section 6.3.9](#).
- 4 Telephone visit for Arm 1 participants who did not receive 6 months of SOC. If concerning symptoms are reported in the opinion of the site investigator, the patient should be seen in person and the conditional evaluations noted in the SOE performed.

7. Section 6.2.3 Post-Entry Evaluations

The revision below has been made to update the study duration for follow-up:

Post-Treatment Evaluations

Arm 1: The window for study visits during weeks 17-26 is ± 3 days. The window for study visits during weeks 34-65 is ± 7 days. **The window for study visits during weeks 66 - 117 is ± 14 days.**

8. Section 6.3, Instructions for Evaluations

The following evaluation has been added:

6.3.18 TB Symptom Assessment

At weeks 30, 38, and 60, participants in Arm 1, who have not already been referred for 6 months of SOC, will have telephone follow-up visits to assess participants' TB symptoms and determine if it is clinically indicated that the participant should come in for an in-person visit and further TB treatment. If the participant has symptoms concerning for TB in the opinion of the site investigator, an unscheduled in-person visit should be conducted within 1 week to determine if PPTR reporting and evaluations are appropriate, and whether the participant should be referred to the local TB program for 6 months of SOC treatment.

9. Section 10.5.1, Interim Monitoring Guidelines

The first and last sentences have been updated as follows:

Unfavorable Composite Outcome Monitoring in Arm 1

Monitoring for unfavorable composite **clinical efficacy** outcome (per definition 10.2.4A) will begin approximately 1 month after the first participant completes treatment in Arm 1 and will continue approximately monthly and for each DSMB review until the end of the study. Two-sided 95% confidence bands for the cumulative probability of unfavorable outcome over time will be generated. If the lower confidence band for the cumulative probability exceeds 12% at any time, this will trigger a DSMB review. **At all DSMB reviews, the DSMB will also be provided with the cumulative probability of unfavorable composite outcome (and corresponding two-sided 95% confidence interval) according to definition 10.2.4B.**

10. Section 10.5.2, Interim Analysis Plan

The first and third sentences have been revised to read:

Confidence Bands for Unfavorable Composite Outcome Probabilities

Monitoring of the unfavorable composite outcome will be according to definition 10.2.4A. only include treatment failures, treatment extensions, loss to follow-up while culture positive, recurrences, and deaths. Two-sided 95% confidence bands will be

generated for the cumulative unfavorable composite outcome probability in Arm 1. Since Arm 2 data will be lagging 3 months behind Arm 1, the **data** will be presented alongside historical unfavorable proportions for SOC on the REMox, OFLOTUB, and RIFAQUIN trials, and A5362 SOC data as it becomes available. There will be no adjustment to the confidence bands for multiple looks.

11. Appendix I-C, ADDENDUM TO SAMPLE INFORMED CONSENT

An addendum to the Sample Informed Consent has been added as Appendix I-C. Appendix I-C is included in this LOA on pages 9-12.

12. Protocol Signature Page (PSP)

A PSP is appended for submission to DAIDS Protocol Registration System (DPRS) as part of the LOA registration packet.

### Version History

Version	Changes Made	Date Finalized
1	Original Version (protocol v1.0, LOA #1, LOA #2)	6/2/2021
1.1	Minor version update for LOA #3. No changes necessary.	February 1, 2022
2.0	Revised to align with protocol v2.0 and CM #1.	January 10, 2023
3.0	

Revised to align with protocol v2.0 and LOA #1

Details added to reflect early close to accrual and data that will contribute to the primary analysis report

Revisions to analysis specifications for time to event outcomes

Additional details added for some outcome measures for clarity

Edits throughout to remove redundant or duplicated information

Updated writing team members and statisticians

	October 13, 2023

## Introduction

### 1.1 Purpose

This Primary Statistical Analysis Plan (SAP) describes the primary and key secondary estimands and other outcome measures that will address specific study objectives and interim monitoring of the A5362 study. The Primary SAP includes general approaches for all primary estimands, key secondary estimands, and other outcome measures in the primary manuscript(s) or submitted to ClinicalTrials.gov (regardless of the reporting timeline). The Primary SAP facilitates discussion of the statistical analysis components among the lead study investigators and statisticians, helping them agree on the statistical analyses to be performed and presented in the primary analysis report.

Detailed outlines of tables, figures, and coding descriptions that will be included in the primary analysis report are included in the Analysis Implementation Plan (AIP). Outlines of analyses for the exploratory objectives and exploratory outcome measures (which we do not describe in the Primary SAP) are provided in a separate SAP.

## 2 Study Overview

### 2.1 Overview of Study Design

A5362 is an open-label, randomized phase IIc study to evaluate whether a 3-month regimen of rifapentine/isoniazid/pyrazinamide/ethambutol (PHZE) with clofazimine (CFZ) dosed as 100 mg daily with a 2-week 300 mg daily loading dose is superior to the standard of care (SOC) 6-month regimen of rifampin/isoniazid/pyrazinamide/ethambutol (RHZE) for DS-TB with respect to (1) early bacteriologic efficacy defined as time to culture conversion by 12 weeks post-randomization and (2) safety over 65 weeks.

Participants will be randomized to one of three treatment arms; Arm 1 with treatment for 13 weeks (including a 2-week CFZ loading dose of 300 mg daily; Arm 2 with treatment for 26 weeks; or Arm C with treatment for 4 weeks with an experimental regimen and the remaining 22 weeks with SOC (PK subgroup)).

- Arm 1 (Experimental): PHZE + CFZ 300 mg once daily for 2 weeks, PHZE + CFZ 100 mg once daily for 6 weeks; then PHZ + CFZ 100 mg once daily for 5 weeks
- Arm 2 (SOC): RHZE for 8 weeks; then RH for 18 weeks
- Arm C (PK subgroup): PHZE + CFZ 100 mg once daily for 4 weeks; then on study, off study medications and treated according to SOC (RHZE for 4 weeks; RH for 18 weeks)

We will follow all participants in Arms 1, 2, and C from randomization to week 65 for the primary and secondary objectives. Protocol v2.0 LOA #1 also includes extended follow-up for some participants corresponding to new exploratory objectives which will be detailed in a separate SAP.

Participants who consent to intensive PK sampling visits will be randomized to Arms 1, 2, or C in a 2:1:1 ratio, respectively, while participants who do not consent to intensive PK sampling will be

randomized only to Arms 1 or 2 in a 2:1 ratio, respectively. We will stratify randomization based on HIV status and the presence of advanced disease as determined by chest X-ray. We will balance randomization by institution.

The primary efficacy analysis will be a superiority comparison of time to liquid culture conversion through 12 weeks in Arm 1 compared with Arm 2. The primary safety analysis will estimate and compare the proportions of participants who have a Grade 3 or higher safety event that is at least one grade higher than baseline at any time during the study. Important secondary analyses include 65-week favorable composite efficacy outcome, including cumulative relapse proportion versus 6-month SOC controls; and safety and tolerability (regimen discontinuation) in Arms 1 and 2.

The primary completion date for A5362 is the final visit date that is included in the primary safety analysis, which will occur approximately 65 weeks after the last participant enrolls. With the early closure to accrual in June 2023, the primary analysis report forming the basis of the primary manuscript will occur earlier than the original planned timepoint. We will prepare the primary analysis report using data collected at visits up to and including the date when the last enrolled participant completes the week 26 study visit. We will later conduct a supplemental analysis using data through week 65, which will form the basis of a secondary manuscript and the clinicaltrials.gov requirements.

## **2.2 Hypotheses**

A 3-month regimen of rifapentine/isoniazid/pyrazinamide/ethambutol (PHZE) with clofazimine (CFZ) dosed as 100 mg daily with a 2-week 300 mg daily loading dose (Arm 1) will demonstrate early efficacy (time to 12-week liquid culture conversion) relative to standard of care (SOC) (RHZE; Arm 2), and will have acceptable safety and tolerability.

## **2.3 Study Objectives**

This Primary SAP addresses the following primary and secondary objectives listed in the study protocol. We address other study objectives outlined in the protocol in subsequent secondary analysis plans.

We will analyze the primary efficacy objective below (2.3.1.1) using a superiority framework based on a one-sided 0.05 alpha level test. For analyses of other objectives, we will present estimates of the parameter of interest alongside their respective two-sided confidence intervals, as specified in Section 5.

We will finalize all analyses for the primary analysis report once the last enrolled participant has completed the week 26 study visit and all queries have been resolved.

### 2.3.1 Primary Objectives

- 2.3.1.1 To compare time to 12-week liquid culture conversion for Arm 1 with Arm 2 (SOC controls).
- 2.3.1.2 To compare the proportion of adverse events (safety) over 65 weeks between Arm 1 and Arm 2 (SOC controls).

### 2.3.2 Secondary Objectives

Each is a comparison between Arm 1 and Arm 2 unless otherwise specified.

- 2.3.2.1 To compare proportion of participants who experience a favorable composite efficacy outcome at 65 weeks between Arm 1 and Arm 2 participants
- 2.3.2.2 To compare premature regimen discontinuation (tolerability) between Arm 1 and Arm 2 participants
- 2.3.2.3 To estimate and compare CFZ-associated increases in QT interval (QTcF, using the Fridericia correction)
- 2.3.2.4 To estimate and compare time to stable liquid and solid mycobacterial culture conversion
- 2.3.2.5 To compare proportion of participants with liquid and solid culture conversion at weeks 8 and 12 between Arm 1 and Arm 2 participants
- 2.3.2.6 To compare days to positivity in automated liquid mycobacterial culture over treatment time
- 2.3.2.7 To compare chest radiographic score (with specific attention to resolution of cavitary disease) between Arms from baseline to end of treatment (Arm 1, week 13; Arm 2, week 26) between Arm 1 and Arm 2 participants
- 2.3.2.8 To compare proportions of participants who experience a favorable clinical/bacteriologic treatment outcome at 65 weeks between Arm 1 and Arm 2 participants
- 2.3.2.9 To estimate cumulative relapse and recurrence proportions up to week 65 for participants on Arm 1 and Arm 2
- 2.3.2.10 To determine CFZ pharmacokinetic (PK) parameters in plasma in Arm 1
- 2.3.2.11 To compare PK parameters when CFZ is given with a loading dose in Arm 1 and without a loading dose in Arm C
- 2.3.2.12 To objectively and subjectively assess CFZ-associated skin hyperpigmentation between Arm 1 and Arm 2 participants

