3.2.3 QT interval

We derive the outcome measures defined below from ECG readings, which the site conducts in triplicate (three ECGs 5-10 minutes apart). We will use the mean of all measurements (up to 3) that are readable and available.

3.2.3.1 Mean baseline QTcF and change from baseline in mean QTcF at weeks 2, 8, and end of treatment (EOT) (Arm 1, week 13; Arm 2, week 26)

3.2.3.2 Occurrence of absolute QTcF  $\geq 480$  ms and  $< 500$  ms, and  $\geq 500$  ms, at any time during study treatment

3.2.3.3 Occurrence of QTcF change from baseline of  $\geq 30$  ms and  $< 60$  ms, and  $\geq 60$  ms, at any time during study treatment

3.2.4 Time to stable culture conversion in liquid and solid media through week 65

Defined as the first of two (consecutive or non-consecutive) negative sputum cultures without an intervening positive culture, and/or visits wherein the participant is unable to produce sputum and has no signs of active TB. Conducted separately for liquid and solid media.

3.2.5 Proportion of participants with culture conversion at weeks 8 and 12 across all study arms.

Liquid (MGIT) and solid media analyzed separately.

3.2.6 Time (days) to positivity in liquid culture (MGIT) after start of treatment through week 65

We will report the median (Q1, Q3) times to positivity in liquid culture at each time point (weeks 1, 2, 3, 4, 6, 8, 10, and 12) in Arm 1 and Arm 2.

3.2.7 Change in chest X-ray (CXR) score from baseline to end of treatment (EOT).

Sites conduct the baseline chest X-ray during screening. We will compute the chest X-ray score with the following validated formula (Ralph et al. Thorax 2010):

CXR Score = percent of total lung affected by any pathology + 40 (if cavitation is present).

We will compute the CXR scores based on both site assessment of the chest X-ray and an assessment by independent central reviewers blinded to study treatment.

- 3.2.8 Proportion of participants with one or more serious adverse events (SAEs) through week 65
- 3.2.9 Proportion of participants who have a TB relapse from EOT until week 65  
For participants who had successful culture conversion through the end of study treatment, TB relapse is defined as a recurrence of TB emanating from the same strain as the participant's originally diagnosed TB, which will be determined through molecular genotyping.

- 3.2.10 Proportion of participants who have a TB recurrence from EOT until week 65
- 3.2.11 Plasma pharmacokinetic parameters for CFZ

Arm 1

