#### 4.1.1 Analysis set definitions

##### 4.1.1.1 Analysis sets (used for primary (5.1.1) and key secondary (5.1.2) estimands):

- **Efficacy Set:**  
All participants who are randomized to study treatment and are not late exclusions.  
(Participants will be late exclusions if they do not have any positive culture (liquid or solid) at screening, entry, or week 1, or if they have TB that is RIF-resistant or INH-resistant identified at screening or entry.)
- **Safety Set:**  
All participants who start assigned study treatment.
- **Start treatment/not late exclusion set:**  
All participants who start assigned study treatment and are not late exclusions.
- **Alive/adequate treatment set:**  
All participants who complete an adequate course of treatment as defined within Sections 10.2.5 and 10.2.6 of the protocol and who do not die during treatment.
- **Per protocol Set:**  
All participants who start and complete assigned study treatment.

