#### **5.1.3.7 Chest X-Ray Scores (Objective 2.3.2.7; Outcome Measure 3.2.7)**

Each participant will have a CXR Score computed at screening and at EOT (week 13 for Arm 1; week 26 for Arm 2). We will compute the difference in scores from baseline to EOT between arms in the efficacy set using linear regression, with adjustment for stratification factors of HIV status and advanced disease status.

We will carry out two analyses for this outcome; (1) based on the site reading of CXR, and (2) based on the central reading of CXR. The central reading will take precedence when presenting results.

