## 6.7 Secondary Outcome Measures

- Proportions in each arm, and difference in proportions with corresponding confidence interval for outcome measures 3.2.1A and B, 3.2.2, 3.2.5, 3.2.6, 3.2.9, 3.2.10.
- Contrasts that estimate the difference between mean change in QTcF scores between Arm 1 and Arm 2 from screening to weeks 2, 8, and 13 with corresponding 95% confidence intervals (outcome measure 3.2.3.1)
- Odds ratio and 95% confidence interval from proportional odds model for outcome measures 3.2.3.2 and 3.2.3.3. If proportional odds model does not hold, then difference in proportions for categories QTcF  $\geq 480$  ms and QTcF  $\geq 500$  ms between arms with corresponding 95% confidence intervals.
- Kaplan-Meier curves of time to culture conversion in liquid media, and solid media, censored at 26 weeks (outcome measure 3.2.4).
- Hazard ratio and 95% confidence intervals for time to culture conversion in liquid media, and solid media, censored at 65 weeks (outcome measure 3.2.4).
- Hazard ratio and 95% confidence intervals for time to positivity in liquid media at each time point. If proportional hazards does not hold, then we will report log-rank test. Side-by-side box plots of time to positivity (Days) at each time point (weeks 1, 2, 3, 4, 6, 8, 0, 12) (outcome measure 3.2.6)
- Estimates for changes in chest x-ray score in each arm from screening to EOT, and estimate of difference in change with 95% confidence interval (outcome measure 3.2.7)
- Contrasts that estimate the difference with corresponding 95% confidence interval between Arm 1 and Arm 2 for the change in total skin hyperpigmentation color difference from week 0 to each of weeks 8, 13, 26, and 65 at each of the following locations; (1) left cheek, (2) right cheek, (3) forehead, (4) chin, (5) using the location with the maximum change in total skin hyperpigmentation color difference. (outcome measure 3.2.12)
- Contrasts that estimate the difference in mean subjective 'change in coloration score' at each of weeks 0, 8, 13, 26, and 65 in Arm 1 vs Arm 2 with corresponding 95% confidence intervals (outcome measure 3.2.13)  
Contrasts that estimate the difference in mean subjective 'distress to skin coloration' score at each of weeks 0, 8, 13, 26, and 65 in Arm 1 vs Arm 2 with corresponding 95% confidence intervals (outcome measure 3.2.12)

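### SAP objective 2.3.2.7 singles out resolution of cavitary disease, but the SAP specifies only the change in a total X-ray score, in which cavitation is never separated from percent of lung affected

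*SAP*

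**What the plan says.** SAP 2.3.2, objective 2.3.2.7, is "To compare chest radiographic score (with specific attention to resolution of cavitary disease) between Arms from baseline to end of treatment" (EOT). EOT is week 13 in Arm 1 and week 26 in Arm 2.

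The sections that implement it read as follows.

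- **SAP 3.2.7** has a single outcome measure, "Change in chest X-ray (CXR) score from baseline to end of treatment (EOT"), with the formula "CXR Score = percent of total lung affected by any pathology + 40 (if cavitation is present").
- **SAP 5.1.3.7** gives the analysis: "We will compute the difference in scores from baseline to EOT between arms in the efficacy set using linear regression", adjusted for HIV status and advanced disease. It is run twice, "1) based on the site reading of CXR, and (2) based on the central reading of CXR", and the central reading takes precedence. The two runs differ only in who read the film.
- **SAP 4.1.1.1** defines the efficacy set: "All participants who are randomized to study treatment and are not late exclusions". It is not limited to participants with a cavity at screening.
- **SAP 6.7** lists the output: "Estimates for changes in chest x-ray score in each arm from screening to EOT", plus the between-arm difference with a 95% confidence interval.
- **SAP 6.2** adds only a baseline table of agreement between site and central classification of advanced disease.

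SAP 2.3 plans estimates with two-sided confidence intervals, as specified in Section 5, for every objective except primary efficacy.

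**The concern.** The objective names one radiographic feature for particular attention. No outcome measure, analysis or listed output in the SAP isolates that feature. Cavity resolution is not defined, no denominator of participants with a cavity at screening is set, and the two parts of the score are not reported separately.

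A reader of the results would get one number made of two parts. It could not show whether the arms differed in cavities, in extent of lung disease, or in both in opposite directions. Participants without a cavity at screening cannot show resolution, yet they are averaged in, so a given difference in resolution moves the score less when fewer participants have cavities.

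The practical stake is interpretation. Letter of Amendment #1 reports that accrual closed because of a high rate of treatment failure and recurrence, so readers will want to know the cavity status at the end of each regimen. If the definition is not fixed in advance, the choice of reader, denominator and handling of new cavities will be made after the data are seen.

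**Working it through.** The plan states no sample size, power or expected value for this outcome, so there is no figure to reproduce. The check is algebra on the SAP's own formula, followed by the precision of a separate estimate.

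**1. Decomposition.** Let change be EOT minus screening, so that a negative value is improvement. From the formula in SAP 3.2.7:

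difference in mean score change (Arm 1 − Arm 2) = difference in mean change of percent lung affected + 40 × difference in change of cavity prevalence.

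Let *c* be the proportion with a cavity at screening (taken as equal in both arms) and *r1*, *r2* the proportions of those who have none at EOT. With no new cavities, cavity prevalence changes by −*c* × *r* in each arm, so

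cavity part = −40 × *c* × (*r1* − *r2*).

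The 40 and the additive form come from the SAP. The documents do not give *c*, *r1* or *r2*; the values below are illustrative.

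**2. One score difference, three different cavity results.** Take *c* = 0.50 and a total difference of −4 points, in favour of Arm 1.

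| Resolution, Arm 1 v Arm 2 | Cavity part | Lung part needed for −4 |
|---|---|---|
| 50% v 30% | −40 × 0.5 × 0.20 = −4 | −4 − (−4) = 0 |
| 30% v 30% | −40 × 0.5 × 0 = 0 | −4 − 0 = −4 |
| 30% v 50% | −40 × 0.5 × (−0.20) = +4 | −4 − 4 = −8 |

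The same result fits better, equal or worse cavity resolution in Arm 1. Other assumed rates change the size of the parts, but one number still cannot determine two.

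**3. Averaging over participants without cavities.** A 20-percentage-point advantage in resolution (50% v 30%) moves the mean score by 40 × *c* × 0.20 points: 2.4 at *c* = 0.30, 4.0 at 0.50 and 5.6 at 0.70.

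**4. Precision of a separate cavity estimate.** Assume *c* = 0.60 and resolution of 30% v 55%. The 95% half-width is 1.96 × √[0.30 × 0.70/*m1* + 0.55 × 0.45/*m2*], where *m1* and *m2* are the numbers with a cavity at screening. The numbers actually enrolled are not given, so two sizes are shown.

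- **99 v 50 participants** (about 90% of the 110 v 55 planned in SAP 2.4): *m1* = 59.4, *m2* = 30. Half-width = 1.96 × √(0.00354 + 0.00825) = 1.96 × 0.1086 ≈ 0.21.
- **55 v 28 participants** (about half of plan): *m1* = 33, *m2* = 16.8. Half-width = 1.96 × √(0.00636 + 0.01473) = 1.96 × 0.1452 ≈ 0.28.

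At the smaller size the half-width exceeds the assumed 25-point difference.

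**The case against.** The strongest reply is that the object of comparison in 2.3.2.7 is the score, with cavities mentioned only in parentheses. The score, which SAP 3.2.7 describes as validated, gives a cavity the weight of 40% of the lung, and that weight could itself be the special attention. This stands in part. A reader might infer that the SAP ignores cavities, and that would be wrong, because they enter every score. The weighting still does not let anyone read cavity resolution off the result, and resolution is what the objective names.

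A reader might also infer that cavity resolution will never be estimated. The documents do not support that. SAP 1.1 leaves detailed table outlines to an Analysis Implementation Plan that was not supplied, SAP 6 presents its list as a minimum, and the only protocol document supplied is Letter of Amendment #1, which does not deal with chest X-rays. The gap is established within this SAP only. It remains a gap, because SAP 1.1 assigns the general approach for outcome measures to the SAP.

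A third tempting reading is that the score analysis lacks power to detect a cavity difference that a dedicated test would find. That argument should not be made. SAP 2.3 plans estimates with intervals for this objective, not tests. Any power figure would need resolution rates and a standard deviation that the documents do not give, and a sample size that early closure makes uncertain.

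Finally, failure, relapse and recurrence have their own outcome measures (SAP 3.2.1, 3.2.9, 3.2.10), and the films are taken 13 weeks apart. Both points stand. They limit what a cavity comparison can say about the regimens, and a difference could partly reflect the later film in Arm 2.

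**Conclusion.** The concern holds in a limited form. The SAP's only X-ray estimate mixes cavitation with percent of lung affected and cannot answer the part of objective 2.3.2.7 that concerns cavity resolution. That conclusion follows from the score formula and does not depend on assumed rates. The illustrations (a 4-point difference compatible with resolution 20 points better, equal or 20 points worse in Arm 1) rest on an assumed 50% with cavities at screening, equal prevalence in the arms and no new cavities.

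The consequence is confined to one descriptive secondary objective. The primary efficacy and safety analyses are unaffected, and the total score remains a legitimate summary. The documents do not support a claim that a cavity difference exists, that it would explain the failures and recurrences, or that it would be a time-matched comparison of the regimens. The amendment should be made because it is cheap and lets the SAP answer its own objective.

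**What to change.** Keep the total-score analysis and add two component estimates to SAP 3.2.7, 5.1.3.7 and 6.7, with the central reading taking precedence as it already does.

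1. **Cavity resolution.** Among efficacy-set participants with cavitation on the screening film, estimate the proportion with none at EOT: Arm 1 minus Arm 2 with a 95% confidence interval. Use the stratification factors of 5.1.3.7 (HIV status and advanced disease) where cell sizes allow. Show by arm the number with a missing EOT film. Show separately the number with new cavitation at EOT among those without it at screening.
2. **Extent of disease.** Estimate change in percent of lung affected with the same regression as for the total score.

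Label all three results as status at each arm's own SAP-defined end of treatment (week 13 v week 26), not as a time-matched comparison.

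The cost is a few sentences and one small table. Both components must already be read on both films to compute the score, so no new data are needed. The drawbacks are that only participants with a cavity at screening contribute to the first estimate, which will have the wide interval shown above, and that it adds another descriptive secondary estimate without a formal test.
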